AE-QoL (subjects ≥ 18 years) and WPAI-GH (subjects ≥ 16 yrs)	X	X	X	X	X	X	X	
EQ-5D-5L	X			X			X	
SGART and IGART ^O				X			X	
Review eDiary data (entered by subject) and assess / document HAE attacks	X	X	X	X	X	X	X	X ^P
eDiary deactivation							X ^Q	X ^P
Confirm access to on-demand HAE medication ^R	X	X	X	X	X	X	X	
IRT investigational product kit assignment	X	X	X	X	X	X		

SC administration of investigational product	X ^S	X ^T						
Investigational product accountability	X	X	X	X	X	X		
Offer subject option to enroll in Study CSL312_3002						X ^B		

Abbreviations: AE-QoL = Angioedema Quality of Life; C1-INH = C1-esterase inhibitor; C4 = complement C4; ECG = electrocardiogram; eCOA = electronic clinical outcomes assessment; EQ-5D-5L = EuroQoL Group 5-Dimension 5-Level; FXII = Factor XII; FXIIa = activated Factor XII; HAE = hereditary angioedema; ICF = informed consent form; IGART = Investigator's Global Assessment of Response to Therapy; IRT = interactive response technology; PK / PD = pharmacokinetic / pharmacodynamics; PRO = patient reported outcomes; SC = subcutaneous; SGART = Subject's Global Assessment of Response to Therapy; WPAI:GH = Work Productivity and Activity Impairment: General Health; yrs = years.

Footnotes to the Schedule of Assessments: Treatment Period [All Subjects]

- A: Treatment Period Visits have \pm 4 day window, with a maximum of 33 days between any 2 consecutive doses.
- B: The Day 182 End of Treatment Period Visit corresponds to the first day of the open-label phase 3b study for subjects rolling-over into Study CSL312_3002. Subjects will enter Study CSL312_3002 after completing the Day 182 assessments and signing the ICF for Study CSL312_3002. Subjects not entering Study CSL312_3002 will be required to complete the Day 242 study visits after completing the Day 182 assessments.
- C: Subjects who terminate early from the study (ie, before Day 182) will undergo the assessments specified for the End of Treatment Visit (Day 182), if possible.

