1	Subject's Global Assessment of Response to Therapy (SGART)	Comparison of the distribution of responses to therapy between CSL312 and placebo at the end of the Treatment Period (Day 182 or Day 91 if discontinuation occurs before Day 182) based on the proportions of subjects with a "excellent, good, fair, poor or none" response to therapy.
Safety Endpoints		
2	
 • AEs • AESIs • SAEs • CSL312 induced anti-CSL312 antibodies • Clinically significant abnormalities in laboratory assessments (ie, laboratory abnormalities reported as AEs). 	The number and percentage of subjects experiencing the specified safety events on treatment with CSL312 or placebo during the entire Treatment Period until Follow-up or Final Visit.

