For the analysis of the time-normalized number of moderate and/or severe HAE attacks, an analogue calculation will be done using all HAE attacks classified as moderate or severe.

The SGART will be presented descriptively. Comparison of the distribution of responses to therapy between CSL312 and placebo at the end of Treatment Period (Day 182) will be done.

To test for a difference in SGART between CSL312 and placebo, a comparison of the distribution of responses at the end of Treatment Period (Day 182) will be performed by using a two-sided Wilcoxon Test (alpha= 5%).

In addition, the secondary endpoints described above (except the SGART) will be summarized for the first 3 months (Day 1 to Day 91), as well as the second 3 months of the Active and Placebo Arms. Further, the following endpoints will be compared between the Active Arm and the Placebo Arm using the first 3 months (Day 1 to Day 91), as well as the second 3 months (Day 92 to Day 182) in an exploratory manner using the same tests as for the respective main analyses:

- Time-normalized number of HAE attacks per month.
- Percentage reduction in the time-normalized number of HAE attacks.
- Percentage of subjects with a percentage reduction of 100%.
- HAE attacks per month requiring on-demand treatment.

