4.6.3 Independent Data Monitoring Committee

An independent data monitoring committee (IDMC) will be established to monitor the safety and efficacy data generated during the study. The IDMC will consist of an independent statistician and clinical specialists in the fields of HAE management, who also have experience in clinical trials. The IDMC will review accumulating data from the ongoing study. Based on these reviews, the IDMC will advise on the further conduct of the study. No success or futility thresholds will be set for the IDMC reviews; CSL will not stop the study unless a major safety issue has been identified. The composition, activities, and responsibilities of the IDMC will be described separately in the IDMC charter. A separate IDMC SAP and IDMC TFL Shells will be created.

5 Changes from the Protocol Planned Analyses

Estimand definition has been updated to reflect the potential impact of the ongoing coronavirus disease 2019 (COVID-19) pandemic, see [Section 7.1](#) and [Section 10.1.1](#).

Comparison of the distribution of responses to therapy between CSL312 and placebo at the end of the Treatment Period will use the ~~cci~~ at Visit Day 182 only. If subject's Study Visit Day 182 ~~cci~~ value is missing the subject will not be included in the ~~cci~~, see [Section 10.4](#).

Also, hypothesis H02 and hypothesis H04 have been defined more clearly by modifying the wording, see [Section 4.2](#).

There are no further changes to the analyses planned compared to the CSP. Any changes conducted after finalization of the SAP will be noted in the Clinical Study Report.

6 Study Analysis Sets

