10.3.2 Secondary Efficacy Analysis

Secondary efficacy endpoints will be analyzed for ITT Analysis Set.

10.3.2.1 The Reduction in the Attack Rate during the Treatment Period compared to the Run-in Period

The secondary efficacy endpoint of the percentage reduction in the time-normalized number of HAE attacks is calculated within a subject as:

$$100 * [1 - (\text{time-normalized number of HAE attacks per month during Treatment Period} / \text{time-normalized number of HAE attacks per month during Run-in Period})]$$

with time-normalized number of HAE attacks per month during Treatment Period as defined in [Section 10.1](#) and with time-normalized number of HAE attacks per month during Run-in Period defined as:

$$[\text{the number of HAE attacks during Run-in Period} / \text{length Run-in Period in days}] * 30.4375$$

where the length of subject's Run-in Period is calculated as:

[Day 1 Visit date of the Treatment Period or Date of Run-in Completion/Non-completion [whichever is first] – Day 1 Visit date of Run-in Period]

for the entire 6-months Treatment Period and will be summarized and tested via a two-sided Wilcoxon Test with alpha = 5%.

The number and percentage of responders and non-responders will be presented with corresponding 95% CIs. A subject is classified as a responder if the percentage reduction in time-normalized HAE attacks is $\geq 50\%$. In addition, the number and percentage of subjects with percentage reductions of $\geq 70\%$, and $\geq 90\%$ will be presented with corresponding 95% CIs.

The number and percentage of subjects with a percentage reduction of 100%, ie, who do not experience a HAE attack and so are attack-free, will be presented and summarized with corresponding 95% CI for the 6-month Treatment Period, a Fisher-Test will be performed to assess for differences between treatment arms.

The number and percentage of subjects who do not experience a HAE attack in the first 3 months after first study drug administration and so are attack-free will be presented and summarized with corresponding 95% CIs. A Fisher-Test will be performed to assess for differences between treatment arms (Hierarchical Testing H03).

The same analysis will be repeated for the second 3 months after first study drug administration.

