10.5 Multiple Comparisons and Multiplicity

Four test one for the primary endpoint (H01) and 3 for the 3 secondary endpoints (H02, H03, H04) will be performed in a hierarchical order with an 2-sided alpha of 5% each, see [Section 4.2](#). Four null hypotheses are defined:

- H01: the time-normalized number of HAE attacks in the first 6-month time period of the Active Arm and in the Placebo Arm period are equal.
- H02: the percentage reduction in means of the time-normalized number of HAE attacks for the 6-months of the Active Arm compared to the 6-month Placebo Arm period are equal.
- H03: the number of subjects who do not experience a HAE attack in the first 3 months of the Active Arm and the first 3-months of the Placebo Period are equal.
- H04: the percent of subjects with good or excellent responses to the ~~cci~~ at the end of Treatment Period (Day 182) are equal for subjects treated with CSL312 and placebo.

The general process flow of the hypothesis testing is as follows:

the null hypothesis associated with the primary endpoint H01 will be tested first. If and only if the resulting 2-sided p-value is < 0.05 , testing of H02 will be performed. If and only if H02 can be rejected (2-sided p-value < 0.05), H03 is tested at 2-sided alpha of 5%. If and only if H03 can be rejected (2-sided p-value < 0.05), H04 is tested at 2-sided alpha of 5%.

This hierarchical testing procedure controls for the overall alpha level of 5%. All other tests will be performed with 2-sided alpha of 5% in an exploratory manner.

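### The SAP limits the global-assessment comparison behind H04 to subjects with a Day 182 value, so an alpha-controlled response percentage is an available-case figure under an ITT label.

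*SAP*

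**What the plan says.** **SAP.** Section 5 lists, as a change from the protocol, that the end-of-treatment comparison uses the assessment "at Visit Day 182 only". If the Day 182 "value is missing the subject will not be included in the" analysis, whose name is blacked out. Section 10.5 defines H04 as equality between arms of "the percent of subjects with good or excellent responses to the" instrument at Day 182. H04 is tested at two-sided 5% once H01 to H03 have been rejected. Section 10.3.2 says "Secondary efficacy endpoints will be analyzed for ITT Analysis Set", and Section 6.2 defines ITT as all randomized subjects. Section 10.3.1 defines no secondary estimand. The missing-value sensitivity analysis in Section 10.1.2 covers the primary endpoint only.

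**Protocol.** The endpoint table in Section 2.2.2 sets the SGART time point as "Day 182 or Day 91 if discontinuation occurs before Day 182". The analysis text in Section 10.3.2.4 says "a comparison of the distribution of responses at the end of Treatment Period (Day 182) will be performed by using a two-sided Wilcoxon Test", and H04 in Section 10.3.2.5 also names Day 182 alone. The SGART is scheduled at Day 91 and Day 182 (Sections 8.7.4.3 and 8.7.4.4). Footnote C of the Treatment Period schedule says early terminators "will undergo the assessments specified for the End of Treatment Visit (Day 182), if possible". Section 4.3.1 encourages subjects who stop treatment to stay in the study to Day 182.

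**The concern.** A response percentage depends directly on its denominator. Leaving the study early is plausibly related to how well a subject thinks the treatment works or is tolerated. Subjects without a Day 182 rating may therefore be less likely to have rated good or excellent than those with one. Omitting them raises the percentage in the arm that loses them and shifts the between-arm difference.

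H04 is the only patient-rated hypothesis under alpha control. As the readable plan stands, its percentages describe subjects with a Day 182 rating while carrying an ITT label, and no visible analysis tests how far the result depends on that. The rule also sets aside Day 91 ratings that the protocol collects and that its endpoint table meant to use.

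**Working it through.** **1. The plan's own figures.** The documents give no response rate, dropout rate or power for H04. The nearest stated figure is for the primary endpoint: about 90% power with 40 completers (24:16) and Poisson means of 0.3125 and 1.3. The O'Brien-Castelloe method gives 90.7% and simulation gives 91.6%, so it reproduces. It does not bear on H04.

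**2. Who is excluded.**

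| Subject | Day 182 value? | In the comparison? |
|---|---|---|
| Completes the study with a rating | Yes | Yes |
| Stops treatment, stays and rates at Day 182 | Yes | Yes |
| Leaves early, rates at termination | Only if stored as nominal Day 182 (not stated) | Unclear |
| Leaves early, Day 91 rating only | No | No |
| No rating at all | No | No |

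SAP 8.2.5 reports data under the nominal visit recorded and applies no windows, so the third row depends on how the termination rating is labelled.

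**3. Bias formula.** In one arm let N be the number randomized, m the number missing, p the available-case proportion and q the proportion good or excellent among those missing. The all-randomized proportion is (1 − m/N)p + (m/N)q. The available-case figure exceeds it by (m/N)(p − q). The error in the treatment difference is therefore

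(m_A/N_A)(p_A − q_A) − (m_P/N_P)(p_P − q_P),

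where A is active and P is placebo. It can take either sign.

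**4. Numbers (assumed).** Sixty subjects at 3:2 give 36 and 24 (SAP 4.5). The responder and missing counts below are assumptions. The test for H04 is blacked out, so Fisher's exact test is also an assumption. Counting missing as non-response sets q = 0.

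| Missing (active, placebo) | Available case | Missing = non-response | Change in difference |
|---|---|---|---|
| 2, 2 | 27/34 vs 9/22: 79% vs 41%, p = 0.005 | 27/36 vs 9/24: 75% vs 38%, p = 0.007 | 38.5 to 37.5 points |
| 5, 1 | 25/31 vs 9/23: 81% vs 39%, p = 0.004 | 25/36 vs 9/24: 69% vs 38%, p = 0.018 | 41.5 to 31.9 points |
| 5, 2 | 24/31 vs 10/22: 77% vs 45%, p = 0.022 | 24/36 vs 10/24: 67% vs 42%, p = 0.068 | 32.0 to 25.0 points |
| 1, 5 | 28/35 vs 8/19: 80% vs 42%, p = 0.007 | 28/36 vs 8/24: 78% vs 33%, p = 0.001 | 37.9 to 44.4 points |
| 4, 8 | 19/32 vs 6/16: 59% vs 38%, p = 0.222 | 19/36 vs 6/24: 53% vs 25%, p = 0.038 | 21.9 to 27.8 points |

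Formula check, second row: (5/36)(0.806) − (1/24)(0.391) = 0.112 − 0.016 = 0.096, matching 41.5 − 31.9 = 9.6 points. Fourth row: (1/36)(0.800) − (5/24)(0.421) = 0.022 − 0.088 = −0.066, so here the SAP rule understates the difference.

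**5. A harsher bound.** Take missing active subjects as non-responders and missing placebo subjects as responders. The second row becomes 25/36 vs 10/24, p = 0.060. The first becomes 27/36 vs 11/24, p = 0.030.

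**The case against.** The strongest reply is that the decisive text cannot be read. SAP Section 10.4, to which Section 5 refers, and the SGART analysis text are blacked out. The exclusion sentence speaks of comparing the distribution of responses, whereas H04 is a percentage. Applying the rule to H04 is the natural reading, but it is an inference. A sensitivity analysis may exist in the hidden text. This stands as a limit on certainty.

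The sponsor can also say that protocol Sections 10.3.2.4 and 10.3.2.5 already name Day 182 alone, so the SAP openly settles an inconsistency. That is true, and nothing here is a hidden deviation. But the protocol's inconsistency does not justify leaving subjects out of the denominator.

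A reader might go further in four ways that the documents do not support:
- **That H04 is a completers analysis.** Subjects who stop treatment but rate at Day 182 stay in. So do early terminators if their rating is stored as nominal Day 182.
- **That the plan expects 20 of 60 to drop out.** The 20 extra subjects are also there for safety data and adolescent recruitment. Forty reaching the end is a floor, not a forecast.
- **That the rule favours CSL312.** The last two rows of the table show the reverse.
- **That the protocol prescribes the early-termination rating first and Day 91 second.** Its endpoint table names only Day 91.

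Finally, H04 is the last step, so H01 to H03 are unaffected.

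**Conclusion.** The point holds in limited form. Followed as readable, the plan gives H04 as an available-case percentage, although SAP 10.3.2 says ITT and the protocol endpoint table supplies a Day 91 fallback. No readable analysis addresses missing H04 values.

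The effect may be small. With two missing values per arm the assumed example moves by 1 point and the conclusion is unchanged. With six or seven missing values spread unevenly it moves by about 7 to 10 points, and in one example p crosses 0.05. Direction and size depend on how many values are missing, in which arm, and how those subjects would have rated. The documents give none of these. The conclusion rests on two inferences: that the blacked-out instrument is the SGART, and that the Section 5 rule applies to H04. It should be corrected, but it does not threaten the primary result.

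**What to change.** For H04, amend the SAP to:

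1. Keep all ITT subjects in the denominator of their randomized arm.
2. State that a rating taken at the Early Termination visit counts as the end-of-treatment value, with Day 91 as the fallback named in the protocol endpoint table. The order is a proposal, and Day 91 will not exist for subjects who leave before it.
3. Count a subject with no rating as not good or excellent.
4. Report the Day 182-only comparison as a sensitivity analysis.

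If the blacked-out text already does this, it is enough to align Section 5 with it.

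The cost is SAP wording, one derivation rule and a little more analysis, all on data the protocol already collects. It should be done before unblinding. Response percentages will be lower by an amount that depends on missingness: 1 missing of 36 takes 80% to 78%, and 5 of 36 takes 81% to 69%. Counting missing as non-response is conservative for each arm's percentage but not always for the difference, which is why the Day 182-only result should be shown beside it.

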6.1 Screened Analysis Set

The screened analysis set comprises all subjects who provide written informed consent and who undergo study screening procedures.

Technical Note: Consider all subjects with an informed consent date collected.

6.2 Intention-to-Treat Analysis Set

The intention-to-treat (ITT) analysis set comprises all subjects in the screened analysis set who were randomized. The ITT analysis set will be analyzed using the treatment to which the subject was randomized, regardless of the treatment actually received.

Any subject who receives a treatment randomization number will be considered to have been randomized.

6.3 Safety Analysis Set

The safety (SAF) analysis set comprises all subjects in the ITT analysis set who received at least 1 dose of investigational product and will be analyzed using the actual treatment received.

6.4 Per Protocol Analysis Set

The per-protocol (PP) analysis set comprises all subjects in the ITT analysis set who receive at least 1 dose of investigational product and who comply with the protocol. Decisions regarding exclusion from the PP analysis will be made and documented before the study data

are unblinded.

6.5 Pharmacokinetic Analysis Set

The PK analysis set comprises all subjects in the safety analysis set with at least 1 measurable concentration of CSL312. PK analysis set will be analyzed using the actual treatment received.

6.6 Pharmacodynamic Analysis Set

The PD analysis set comprise subjects in the safety analysis set for whom at least 1 PD measurement was obtained. PD analysis set will be analyzed using the actual treatment received.

7 General Considerations

Datasets will be created according to Clinical Data Interchange Standards Consortium (CDISC) standards. Study data will be provided in Study Data Tabulation Model (SDTM) format. Analysis data will be provided in Analysis Data Model (ADaM) format.

SAS version 9.4 or higher will be used to perform all data analyses and to generate Tables, Figures and Listings (TFLs).

All ICH required data in the database will be presented in data listings.

Depending on the analysis sets, all data from a subject or a subset of data may be excluded from certain analyses as defined in [Section 9.2](#) (e.g., analyses based on the PP Analysis set).

Summaries of continuous variables will be in terms of the number of missing and non-missing observations, mean (with respective 95% confidence interval (CI), if applicable), standard deviation, median, first quartile (Q1), third quartile (Q3), minimum and maximum.

Categorical variables will be summarized using counts and percentages.

Analyses that use other descriptive statistics will be defined and described in the applicable SAP section.

Summary statistics of location parameters (e.g., mean, median, quartiles) will be reported to one more decimal place than the collected data. Summary statistics of variability (e.g., SD) will be reported to one more decimal place than the commensurate location parameter. For example, the mean and median for age will be reported to one decimal place because it is collected in full years. The SD of age will then be reported to 2 decimal places. Descriptive percentages and proportions will be displayed to one decimal place. Percentages and proportions to be tested will be calculated to 4 decimal places. Durations will be display to 1 decimal place.

The by-subject listings will be sorted by the treatment arm, subject number, and then by visit / date and time, or item number (if applicable).

Formatting for dates and times will be:

- Dates only – ddmmmyyyy;
- Times only – hh:mm or hh:mm:ss (as appropriate);
- Dates and times – ddmmmyyyy hh:mm or ddmmmyyyy hh:mm:ss (as appropriate).

Generally, only data of pre-specified planned visits will be used in statistical summary analyses, and calculations of any derived parameters; data of unscheduled visits will be included in the listings only.

Actual, rather than planned, sampling time points will be used in the derivation of PK parameters and in the individual concentration-time plots and listing of PK concentration data. Planned sampling time points will be used in the descriptive summaries and in mean and median plots. Concentration-time data will be listed according to actual sampling time points relative to dosing time.

Assessment windows will not be defined for classifying measurements obtained outside scheduled assessment times.

7.1 **Coronavirus Disease 2019 (COVID-19) Impact**

As it is expected that the COVID-19 pandemic will be ongoing during the conduct of the study, the impact of COVID-19 will be assessed and reported.

Primary Estimand

The primary estimand is defined in [Section 10.1.1](#) and is taking into account intercurrent events such as:

- missed doses which might be caused by issues in the drug delivery to the patient due to COVID-19, the COVID-19 disease itself or COVID-19 vaccination scheduling/side effects (intercurrent event of non-compliance to treatment);
- early treatment or study discontinuation which might be caused by COVID-19 (intercurrent events of early treatment or study discontinuation).

Further events introduced by COVID-19 (for example concomitant medications used to treat COVID-19 or vaccinations) will be assessed in the Blind Data Review Meeting (BDRM) and might lead to an exclusion of a subject or subject's data from the PP Analysis Set which is the study analysis set defined for the supplementary analysis of the primary estimand. HAE attacks

will be also assessed during BDRM if those could be triggered by COVID-19 and decision will be made to exclude those subjects or subject's data from the PP Analysis Set.

Subject Disposition: Study Treatment Discontinuation or Study Discontinuation

Subjects who experience either study treatment discontinuation or study discontinuation due to COVID-19 will have the reason captured in the eCRF. On the appropriate eCRF form for study discontinuation (“Conclusion of Subject Participation” form) or eCRF form for treatment discontinuation (“End of Treatment” form) as reason ‘Pandemic Related’ can be selected. Cases of study treatment discontinuation or study discontinuation due to pandemic will be included in the summary of subject disposition.

Adverse Events

Adverse events associated with COVID-19, which can include a clinically significant laboratory finding like a positive test result for COVID-19, will be reported by investigators. COVID-19 associated adverse events are identified via MedDRA coding. Relevant adverse events will be identified for reporting by the following Standardised MedDRA Query (SMQ): COVID-19 (SMQ). All COVID-19 associated adverse events will be included in standard AE tables.

An overview summary table of COVID-19 associated treatment-emergent adverse events (TEAEs), including number and percentages of subjects as well as the number of events, will be provided for the Safety Analysis Set including for the following:

- Any TEAE (related/not related),
- Serious TEAE (related/not related),
- TEAE resulting in death (related/not related),
- TEAE leading to discontinuation of study treatment (related/not related),
- TEAE leading to study withdrawal (related/not related),
- TEAE by maximum severity (mild, moderate, severe, missing).

The following summary tables will be provided:

- TEAEs occurring within 7 days of COVID-19 vaccine administration by PT, Among Subjects Receiving COVID-19 Vaccination
- TEAEs excluding those occurring within 7 days of COVID-19 vaccine administration by PT.

The following listings of COVID-19 associated adverse events will be provided:

- Any AE,
- AEs within 7 days of COVID-19 vaccine administration.

Concomitant Medications

Concomitant medications used to treat COVID-19 associated adverse events will be flagged in the listing of prior and concomitant medications.

For concomitant medications which are linked to specific adverse events, the eCRF collects information to identify the specific adverse event (e.g., Adverse Event ID). As described in the Adverse Events section, relevant adverse events will be identified by the following Standardized MedDRA Query (SMQ): COVID-19 (SMQ).

For identification of COVID-19 vaccines the WHODrug Standardised Drug Grouping (SDG) ‘*Vaccines for COVID-19*’ will be utilized, based on the WHODrug-Global dictionary version used for coding of prior and concomitant medications.

COVID-19 vaccinations will be listed by subject showing start and end date:time, dose, route, frequency, primary indication for the medication, and concomitant medication flag (Prior, Prior/Concomitant, Concomitant). If the vaccination manufacturer name is provided, it will be listed as well.

Further, a listing will be prepared including the date of COVID-19 vaccinations, along with date and time of previous and subsequent study treatment, date of first HAE attack after vaccination with corresponding HAE ID and date of first AE with AE ID after vaccination for all subjects in the Safety Analysis Set. If the vaccination manufacturer name is provided, it will be added.

Visit Modality and Missed Visits

Changes to subjects’ visits caused by the COVID-19 pandemic will be captured for each subject in the eCRF on the “Visit” form. It can be determined if a visit was not done due to “Epidemic/Pandemic Related (Specify)” or if a visit contact mode/ modality changed due to Epidemic/Pandemic reason (Yes, No). The number of subjects with missed visits or alternate visit modality (e.g., remote visit) due to COVID-19 will be summarized by visit and overall and will be listed.

Protocol Deviations (PDs)

Protocol deviations due to the COVID-19 pandemic will be collected in the Clinical Trial Management System (CTMS) per the study specific Protocol Deviation plan.

Pandemic related protocol deviations are identified within CTMS by using the term “COVID-19” as the first term within the deviation description. In addition, the sub-category of ‘other’ will be chosen.

COVID-19-related protocol deviations will be summarized as sub-categories under existing categories of protocol deviations. All COVID-19 related protocol deviations will appear in the listing of protocol deviations and will be flagged. All PDs will be reviewed during Blinded Data Review Meeting (BDRM, see [Section 9.2](#)).

Overview of COVID-19 Impact

Number and percentages of subjects with at least one of the following due to COVID-19 will be summarized in an overview table:

- Subjects with Any COVID-19 Impact,
- Protocol Deviations,
- Missing Visit,
- Alternate Visit Modality,
- Study Treatment Discontinuation,
- Study Discontinuation,
- Any AEs/TEAEs,
- Any Serious AEs/TEAEs,
- Subjects received COVID-19 vaccine.

